13.0 CRITERIA FOR REMOVAL FROM STUDY

Subjects can leave the study at any time for any reason if they wish to do so without any consequences. The investigator can decide to withdraw a subject from the study for urgent medical reasons. Patients who withdraw before 120 days due to complications will be counted as failures for the patency objective. Patients who withdraw before 30 days will be counted as having experienced a complication for the purposes of the secondary objective.

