14.1 BIOSTATISTICS

The primary objective of this study is to assess biliary drainage patency after IRE treatment of hilar cholangiocarcinoma. In patients with plastic percutaneous drains this is defined as ability to remove plastic biliary drains within 15 months of the IRE procedure without need for reinsertion of a drain or stent. For patients with metal stents in place the definition of patent biliary drainage is 4-months without cholangitis post IRE procedure.

We will enroll 20 patients. Mean patency is approximately 1.5 months for plastic stents and 4 months for metal stents. Assuming an exponential distribution time to failure, we extrapolate that the patency rate at 15 months for plastic stents and at 4 months for metal stents will approximately be 37% and we will use this number as our historical control rate. If 10 or more of the 20 patients we plan to enroll display patency (at 1.5 months for plastic and 4 months for metal stents) then we will recommend IRE for further study. This decision rule has 8% Type I error and 12% Type II error for distinguishing between patency rates of 37% and 65%.

The secondary outcomes of interest are:

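### The primary decision rule (10 or more of 20) has 16.5% type I and 5.3% type II error, not the stated 8% and 12%, which belong to 11 or more of 20

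*Combined protocol and SAP*

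**What the plan says.** Section 14.1 (Biostatistics) sets out a single-arm design with a binary primary endpoint, biliary drainage patency.

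- Sample size: "We will enroll 20 patients".
- Null rate: the section assumes exponentially distributed time to failure and the following means: "Mean patency is approximately 1.5 months for plastic stents and 4 months for metal stents". It concludes that patency at those times "will approximately be 37% and we will use this number as our historical control rate".
- Decision rule: IRE is recommended for further study on the condition "If 10 or more of the 20 patients we plan to enroll display patency".
- Claimed performance: "This decision rule has 8% Type I error and 12% Type II error for distinguishing between patency rates of 37% and 65" per cent.

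The cut-off is stated once, and no other section gives a different one. Section 13.0 adds: "Patients who withdraw before 120 days due to complications will be counted as failures for the patency objective". Section 14.1 replaces patients who consent but do not have the procedure. Neither provision suggests a denominator other than 20.

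**The concern.** For a fixed sample size, cut-off, null rate and alternative rate, both error rates of a single-arm rule are fully determined, so the claim can be checked exactly. It fails in a recognisable way: neither error rate fits the written cut-off, and both fit the next integer up.

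This is the only efficacy criterion for recommending IRE for further study. If the cut-off is right, the protocol reports about half the real false-positive risk. If the error rates are right, the cut-off is one patient too low. A result of exactly 10 of 20 would be positive under the written rule and negative under the rule whose error rates are quoted. A choice between them made after seeing that result would not be credible.

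**Working it through.** **Inputs, all from section 14.1:** n = 20; cut-off r = 10; null rate p0 = 0.37; alternative p1 = 0.65; claimed errors 8% and 12%.

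**Null rate.** For an exponential distribution, survival at the mean is exp(−1) = 0.368. This reproduces the plan's 37%, so the null rate follows from its stated basis.

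**Formulas.** Let X be the number of patients with patency, X ~ Binomial(20, p).

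- Type I error = P(X ≥ r | p = 0.37)
- Type II error = P(X ≤ r − 1 | p = 0.65)

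**Can the claimed 8% and 12% be reproduced?**

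| Cut-off | Type I error at 37% | Type II error at 65% |
|---|---|---|
| 9 or more | 30.0% | 2.0% |
| **10 or more (as written)** | **16.5%** | **5.3%** |
| **11 or more** | **7.8%** | **12.2%** |
| 12 or more | 3.1% | 23.8% |
| Claimed | 8% | 12% |

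Only 11 or more rounds to the claimed pair (0.0775 and 0.1218 before rounding). At the written cut-off, the type I error is 0.165 / 0.08 = 2.1 times the claim, and power is 1 − 0.053 = 94.7% rather than 88%.

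**The difference between the two cut-offs** is the single outcome X = 10:

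- at 37%: 0.1650 − 0.0775 = 0.0875, about 8.8%
- at 65%: 0.1218 − 0.0532 = 0.0686, about 6.9%

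Exactly 10 of 20 is therefore slightly more likely if patency equals the historical control than if it reaches the target.

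**Other ways the claim might have arisen:**

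- *Unrounded null.* With p0 = exp(−1), the type I error at 10 or more is still 16.0%.
- *Normal approximation at r = 10.* It gives 11.4% / 8.0% without continuity correction and 16.5% / 5.0% with it.
- *Different sample size.* Over n = 17 to 23 and r = 8 to 13, only n = 20 with r = 11 rounds to 8% / 12%.
- *Different rates with r = 10.* A type I error of 8% would need a null of about 32.6%, and a type II error of 12% would need an alternative of about 60.4%. Neither rate is in the protocol.

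**The case against.** The arithmetic is not in dispute. The best arguments against the point concern its weight and wording.

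**Which number is wrong is not known.** The protocol says 10 and nowhere says 11. This stands. The fit at the adjacent integer suggests that more than 10 was written as 10 or more, but that is inference. The demonstrable fault is the contradiction.

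**Safety rules can end the trial first.** Section 14.1 also stops the study if 4 or more of the first 8 patients have a qualifying complication, so 16.5% applies to a trial that runs to completion. Assume that complications are independent of patency and that only this rule operates. The overall chance of a false recommendation is then 16.1% at an assumed 16% complication rate and 11.7% at 35%. In the second case type II error rises to 33%. To bring 16.5% down to 8%, safety stopping would have to end about 52% of trials (1 − 0.08/0.165), which would push type II error to about 54%. The safety rules qualify the figure but cannot produce the claimed pair.

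**The effect is small and partly favourable.** Only one outcome changes sides, power is higher than claimed, and a 16.5% type I error may be tolerable in a small phase II study. That is a fair design preference, but it supports stating 16.5%, not 8%. A confidence interval does not settle the choice either: the exact 90% interval includes 37% both for 10 of 20 (30% to 70%) and for 11 of 20 (35% to 74%).

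**The digit may have been misread from the PDF.** The same section shows 15 months where other sections have 1.5, which looks like a lost decimal point. Replacing one digit by another would be a different kind of fault, and nothing points to it. Checking the source PDF is sensible. The 15 does not enter this calculation.

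**Conclusion.** The concern holds: the stated operating characteristics of the primary decision rule are wrong as written. With 20 evaluable patients, independent outcomes and rates of 37% and 65%, the rule of 10 or more has 16.5% type I and 5.3% type II error, against the stated 8% and 12%. The stated pair belongs to 11 or more. The result uses only the protocol's own figures and does not depend on rounding of the null rate or on the method of calculation. It must be corrected, because it concerns the go/no-go criterion for the primary endpoint.

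**What to change.** In section 14.1, make the cut-off and the error rates agree, in one of two ways:

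1. Change the cut-off to 11 or more of 20 and keep the stated errors (exact values 7.8% and 12.2%). The bar for a positive result rises by one patient.
2. Keep 10 or more of 20 and restate the errors as 16.5% type I and 5.3% type II. The protocol then openly accepts about a 1 in 6 chance of a false recommendation.

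The sponsor should say which was intended and record the decision before the primary endpoint is analysed. Neither option needs more patients, further data or any change in conduct.

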- Safety will be assessed by determining the proportion of patients experiencing a clinically relevant complication within 30 days post-IRE, defined as CTCAE (version 5.0) grade 3 or higher complications requiring re-intervention, prolonged hospital stay, intensive care admission, re-admission or leading to mortality. After accruing the first 8 patients, we will do an interim analysis of safety. If 4 or more of these 8 patients experience a grade 3 complication within 30 days post-IRE (as defined above) then the study will stop for lack of safety. A 30 day observation window will follow after the eighth patient is enrolled. If one patient in the first 8 patients has a grade 4 or 5 complication the study will be halted. If none of these conditions are met then we will accrue another 12 patients. If 6 or fewer of the total group of 20 patients have a grade 3 complication we will conclude that the safety endpoint has been met. This safety monitoring rule has an 81% chance of stopping the study early for safety concerns if the true probability of complications is 35%. If there is a death during the 30-day post-procedure period the study will be halted to examine the relationship of death to the procedure. We will examine the cause of death for all 30-day deaths and determine if it could be related to the procedure. If the death can possibly be related to the

procedure then the protocol will be stopped. To continue with the protocol after a death, we will submit to RB all the documentation related to the ascertainment of cause of death and describe how it cannot be related to the RE procedure.

- Duration of hospital stay will be summarized with median, range and quartiles.
- Quality of life will be summarized by average subscale scores at each visit and change from previous visit will also be reported by the same summary statistics.
- Tumor response on CT imaging and blood biomarker response will be reported as a binomial proportion with a 95% confidence interval. RECIST criteria cannot be applied to Klatskin tumors as they are radiographically difficult to assess. This instead will be a subjective evaluation of the ablation zone to determine the appearance of an RE associated ablation zone in the hilar area. This is currently unknown.
- Time between RE and start of palliative chemotherapy will be summarized with median, range and quartiles
- Duration of palliative chemotherapy will be summarized using Kaplan-Meier statistics

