- Progression-free and overall survival will be summarized using Kaplan-Meier statistics
- Success rate of completing RE reported as a binomial proportion with a 95% confidence interval

Expected accrual rate, accrual duration, and study duration

Our anticipated accrual rate is approximately 1 patient per month. This accrual rate is based on analysis of potentially eligible patients seen at our Outpatient Clinic in the last 2 years (2016 and 2017). Thus, it should take approximately 1.5 years to accrue the 20 patients needed for the trial. Allowing for 2 months of follow-up to obtain the primary endpoint on the last patient enrolled and 4 months to assemble, analyze and interpret the data the total study duration is projected to be at most 2 years. Patients who consent to the procedure but do not have it will be considered a screen failure. They will be replaced by another patient and their questionnaire data will be removed from the study.

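### The 4-of-8 grade 3 safety boundary is checked only after the eighth patient is accrued, so up to four patients can be treated on study after the stop decision is already fixed

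*Combined protocol and SAP*

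**What the plan says.** The safety bullet in section 14.1 (Biostatistics) sets a first stage of eight patients: "After accruing the first 8 patients, we will do an interim analysis of safety". The boundary reads "If 4 or more of these 8 patients experience a grade 3 complication within 30 days post-IRE", in which case the study stops for lack of safety. On timing, the bullet adds: "A 30 day observation window will follow after the eighth patient is enrolled". The second stage depends on the result: "If none of these conditions are met then we will accrue another 12 patients".

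Two other halts appear in the same bullet. One concerns severe events: "If one patient in the first 8 patients has a grade 4 or 5 complication the study will be halted". It has no stated time of examination. The other concerns deaths and is driven by the event itself: "If there is a death during the 30-day post-procedure period the study will be halted to examine the relationship of death to the procedure".

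The accrual paragraph of the same section states: "Our anticipated accrual rate is approximately 1 patient per month". Section 13.0 counts a withdrawal before 30 days as a complication.

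No section calls for a running grade 3 count, a pause between patients 1 and 8, or a stop when the fourth event is seen. The general arrangements (registration of complications in section 9.0, data and safety monitoring in section 16, SAE reporting in section 17.3) do not apply the four-event boundary.

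**The concern.** The criterion is a count in a fixed group of eight, and a patient once counted stays counted. Four events among the first seven patients already mean at least four of eight, whatever happens to the rest. A look placed after patient 8 therefore leaves a period in which the protocol's own lack-of-safety criterion has been met while enrolment and on-study treatment may continue. The further outcomes cannot alter the safety decision. At most four patients (numbers 5 to 8) are affected, because the second stage opens only after the look.

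**Working it through.** **Inputs.** Boundary 4 of 8, final limit 6 of 20, and the 35% rate at which the plan evaluates its safety rule (section 14.1). Overall complication rate of 16% from a meta-analysis, and 2 of 26 patients with grade 3 or higher in a series of this disease (section 3.0). Accrual of about one patient per month (section 14.1).

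**The plan's own figure.** Section 14.1 gives an 81% chance of stopping early at 35%. The written count rules do not reproduce it:
- Interim rule alone: P(X ≥ 4), X ~ Bin(8, 0.35) = 29.4%.
- Interim or final rule: P(X₈ ≥ 4) + Σ_{x=0..3} P(X₈ = x)·P(Bin(12, 0.35) ≥ 7 − x) = 61.5%.
- Adding an immediate grade 4-5 halt gives an interim stop of 75.3% if 15 of the 35 percentage points are grade 4-5, and 84.0% if 20 are. The documents give no such split.

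That discrepancy is a separate matter. The calculation below uses the written 4-of-8 rule.

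**When the fourth event occurs.** With independent events at rate p, P(fourth event at patient k) = C(k−1, 3)·p⁴·(1−p)^(k−4). At p = 0.35, p⁴ = 0.0150:
- k = 4: 0.0150 × 1 = 1.5%
- k = 5: 0.0150 × 4 × 0.65 = 3.9%
- k = 6: 0.0150 × 10 × 0.65² = 6.3%
- k = 7: 0.0150 × 20 × 0.65³ = 8.2%
- k = 8: 0.0150 × 35 × 0.65⁴ = 9.4%

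The unrounded sum is 29.4%, equal to P(X ≥ 4) above. Stopping at the fourth event therefore leaves the probability of reaching 4 of 8 unchanged. The part before patient 8 is 20.0%, and 0.1998/0.2936 = 68% of interim stops.

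**Patients treated after the decision is fixed.** Each such trial treats 8 − k more patients. The mean per trial is 4(0.0150) + 3(0.0390) + 2(0.0634) + 1(0.0824) = 0.39. Per trial reaching 4 of 8 it is 0.386/0.2936 = 1.3.

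**Sensitivity to the true rate.** The last column assumes that one further patient is always treated before a complication is known, so 8 − k becomes 7 − k.

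| True rate | P(≥4 of 8) | Fourth event by patient 7 | Share of interim stops | Extra patients per trial | Per stopped trial | Per stopped trial, one-patient lag |
|---|---|---|---|---|---|---|
| 16% | 2.7% | 1.5% | 57% | 0.03 | 0.98 | 0.41 |
| 25% | 11.4% | 7.1% | 62% | 0.13 | 1.12 | 0.50 |
| 35% | 29.4% | 20.0% | 68% | 0.39 | 1.32 | 0.64 |
| 50% | 63.7% | 50.0% | 79% | 1.09 | 1.72 | 0.93 |

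At 2/26 = 7.7% the fourth event falls before patient 8 in 0.1% of trials.

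**Sensitivity to the grade 4-5 halt.** Assume that a share s of the 35% is grade 4-5 and halts the study at once. The fourth grade 3 event then falls before patient 8, with no earlier halt, with probability (0.35(1−s))⁴ × (1 + 4·0.65 + 10·0.65² + 20·0.65³) = (0.35(1−s))⁴ × 13.32:
- s = 10%: 13.1%
- s = 20%: 0.28⁴ × 13.32 = 8.2%, or 0.16 patients per trial
- s = 30%: 4.8%

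The documents do not give s.

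**The case against.** A single safety look after a fixed first stage is a recognised design. The text sets when the analysis is done and does not forbid stopping sooner. Complications are recorded and SAEs reported, so a fourth event would not go unseen. This stands in part: that the boundary is applied only after patient 8 is an inference from silence. But the bullet gives deaths an event-driven halt and gives this count none, and whether to stop should not be left to discretion.

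The conditional figures (68%, 1.3 patients) look larger than the unconditional ones, and 35% is the rate used to evaluate the rule, not an expected rate. This stands, and the unconditional and low-rate figures belong beside them. The assumption that each outcome is known before the next patient is also favourable: 20 patients in about 1.5 years is one per 27 days (1.5 × 365/20 = 27.4), slightly less than the 30-day window. With a one-patient lag the saving roughly halves but does not vanish.

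A reader might infer that stopping at the fourth event would spare patients a laparotomy and IRE. The documents do not support that. Section 4.3 says the study takes data from patients having IRE as standard of care, and section 17.1 says the study does not pay for it. Under section 6.1, some patients undergo exploration for possible resection in any case. Closing accrual ends on-study treatment; it may not prevent the procedure.

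A reader might also infer that patients treated after the fourth event add nothing statistically. They cannot change the 4-of-8 decision, but they do inform the complication proportion, patency and the secondary outcomes. Stopping on an event gives an observed proportion of 4/4 to 4/7 (100% to 57%) in trials settled before patient 8, which overstates the rate. A stop at the fixed look already reports at least 4/8, so an upward bias exists now and would grow somewhat.

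**Conclusion.** The concern holds as a gap in the timing of the grade 3 rule. The plan describes no application of the boundary before patient 8, although the decision can be fixed from patient 4 onwards. At 35%, the size is 20.0% of trials and 0.39 patients per trial, or 1.3 per stopped trial. This assumes independent events, all grade 3, each known before the next patient. A reporting lag or early grade 4-5 halts reduce it (about 8% of trials if a fifth of events are grade 4-5, an assumption). At the 16% rate it is rare, about 1.5% of trials. What is at stake is on-study treatment of up to four patients after the protocol's own safety criterion is met. The exposure is modest, but it can be avoided without altering the boundary, so the change should be made.

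**What to change.** Amend the safety bullet in section 14.1 with one sentence: accrual stops as soon as the fourth qualifying complication is recorded among the first eight treated patients; if fewer than four have occurred, the interim review takes place when all eight have completed 30 days after IRE.

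The boundary and the probability of reaching 4 of 8 stay as they are. The costs are a running tally, which the clinical research coordinator already assigned in section 16 can keep, slightly fewer data in a stopped trial, and a complication proportion biased upward when the trial stops on an event. The report of a stopped trial should say so.

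### The stated 81% chance of stopping early at a 35% complication rate does not follow from the written count boundaries, which give 29% at the interim and 62% over both looks

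*Combined protocol and SAP*

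**What the plan says.** The safety bullet in section 14.1 (Biostatistics) sets out the rule in these parts:

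- **Event.** A clinically relevant complication within 30 days, "defined as CTCAE (version 5.0) grade 3 or higher complications requiring re-intervention" or one of several other consequences.
- **Interim look.** "After accruing the first 8 patients, we will do an interim analysis of safety". The count boundary is "If 4 or more of these 8 patients experience a grade 3 complication within 30 days post-IRE", with a cross-reference back to the definition above; the study then stops.
- **Severe-event halt.** "If one patient in the first 8 patients has a grade 4 or 5 complication the study will be halted".
- **Final look.** Otherwise 12 more patients are accrued. "If 6 or fewer of the total group of 20 patients have a grade 3 complication", the safety endpoint is met.
- **Death halt.** "If there is a death during the 30-day post-procedure period the study will be halted" while its relation to the procedure is examined. The study may continue if the death is shown to be unrelated.

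Section 13.0 adds to the count: "Patients who withdraw before 30 days will be counted as having experienced a complication for the purposes of the secondary objective".

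The performance claimed for the rule is one sentence: "This safety monitoring rule has an 81% chance of stopping the study early for safety concerns if the true probability of complications is 35"%.

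**The concern.** The 81% is given as a function of one number, a 35% complication probability. With a 35% event rate, 2.8 events are expected among 8 patients (8 × 0.35), which is below the boundary of 4. The interim count therefore cannot stop the study most of the time, let alone four times in five.

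The sentence tells the review board that a 35% complication rate would very probably end this surgical study early. If it is wrong, either the protection is overstated or the written boundaries are not the ones that were designed. The text does not show which.

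**Working it through.** **Inputs, all from section 14.1.** Interim n = 8, stop at 4 or more. Second stage n = 12. Safety not met at 7 or more of 20. Complication probability 0.35. Claimed stopping probability 0.81.

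**1. Interim count boundary.**
P(X ≥ 4), X ~ Bin(8, 0.35), is 1 − (0.0319 + 0.1373 + 0.2587 + 0.2786) = **0.294**. The study passes the interim count with probability 0.706.

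**2. Both count boundaries.** Safety is met if x ≤ 3 at the interim and at most 6 − x events follow in the next 12 patients:

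| x of 8 | P(x) | P(≤ 6 − x of 12) | Product |
|---|---|---|---|
| 0 | 0.0319 | 0.9154 | 0.0292 |
| 1 | 0.1373 | 0.7873 | 0.1081 |
| 2 | 0.2587 | 0.5833 | 0.1509 |
| 3 | 0.2786 | 0.3467 | 0.0966 |

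The products sum to 0.385, so the probability of crossing either boundary is **0.615**.

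**3. Counted rate that would give 81%.** Solving the same formulas gives about 59% for the interim alone and about 41.5% for both looks. If counted withdrawals alone closed the gap, they would have to add about 24 points (59 − 35) or 6.5 points (41.5 − 35).

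**4. Adding the grade 4–5 halt.** Let g be the grade 3 rate and q the grade 4–5 rate. Then

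P(stop at interim) = 1 − Σ(x = 0 to 3) C(8,x) g^x (1 − g − q)^(8−x).

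For both looks, multiply each term by P(Bin(12, f) ≤ 6 − x), with f = g + q if the final count includes grade 4–5, or f = g if it counts grade 3 only. The plan gives no q, so the values below are assumptions. With grade 4–5 inside the 35% (g = 0.35 − q):

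| Assumed q | Interim | Both looks, f = g + q | Both looks, f = g |
|---|---|---|---|
| 0.05 | 48% | 71% | 64% |
| 0.10 | 64% | 78% | 70% |

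The q needed to reach 81%:

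| | Interim | Both looks, f = g + q | Both looks, f = g |
|---|---|---|---|
| Inside the 35% | 0.181 | 0.122 | 0.176 |
| On top of a 35% grade 3 rate | 0.132 | 0.046 | 0.071 |

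**5. Which grades are counted.** The definition says grade 3 or higher; both boundaries say grade 3. If the counts are grade 3 only and 5 of the 35 points are grade 4–5 (assumption), steps 1 and 2 at 0.30 give 19.4% and 43.1%.

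**6. A possible source.** Boundaries one count lower (3 or more of 8, 6 or more of 20) give 57.2% at the interim and 80.5% over both looks. The patency rule in the same section shows a similar pattern. As written, 10 or more of 20 gives 16.5% type I and 5.3% type II error at 37% and 65%, whereas 11 or more gives 7.8% and 12.2%, close to the stated 8% and 12%. A one-count mismatch is therefore possible, but not proven. Even then, the interim figure would be 57%.

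**The case against.** The strongest reply is that the claim concerns the whole monitoring rule, and the sentence comes after the grade 4–5 halt, while 29% and 62% cover the counts alone. This is fair. It shows that 81% is underivable, not that it is impossible for the full rule.

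The death halt strengthens the reply, because it is not limited to the first 8 patients. Assume that deaths lie inside the 35%, that there are no other grade 4–5 events, and that every death ends the study. Write d for the death rate and g = 0.35 − d. The probability of stopping or crossing at either look is then 1 − Σ(x = 0 to 3) C(8,x) g^x 0.65^(8−x) × Σ(y = 0 to 6 − x) C(12,y) g^y 0.65^(12−y). This gives 66.6%, 75.1% and 81.7% at assumed death rates of 1, 3 and 5 points. So the grade 4–5 rates in step 4 apply only with the death halt set aside. But these are upper bounds, since the study can resume after an unrelated death, and the death rate is again an assumption. At 5 points, stopping before the final look is still only about 72%.

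Section 11.1 does list expected frequencies, such as 1% for liver failure and 1% for cardiac events. They are not graded and give no grade 4–5, 30-day death or withdrawal rate.

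On the grades counted, the interim boundary's cross-reference favours grade 3 or higher, so the 19% and 43% show only that the wording matters. Finally, safety is a secondary outcome and the halts operate whatever the sentence says. That limits the harm if the boundaries are as intended, but it does not make the sentence correct.

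**Conclusion.** The concern holds. On the written count boundaries, with each counted event independent and at 35%, the chance of stopping early is 29%, and the chance of crossing either boundary is 62%, against a stated 81%. On the same basis the study goes past the interim 71% of the time and meets its safety endpoint 38% of the time. The severe-event halt, the death halt and counted withdrawals could lower both of these figures by an unknown amount. Reaching 81% requires rates that the plan does not state, and the smallest of the grade 4–5 rates also requires counting the 20-patient look as early and letting severe complications exceed 35% in total. This must be fixed, because it is the only stated performance of the safety rule and it may point to a mis-stated boundary.

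**What to change.** The sponsor should reconcile the 81% with the boundaries in section 14.1 and state which is intended. This review does not propose a boundary.

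- **If the boundaries stand:** replace the sentence with 29% at the interim and 62% over both looks, labelled as excluding the grade 4–5 halt, the death halt and counted withdrawals. Give a figure that includes the halts only with its assumed rates declared. Say which looks and halts each figure covers, and whether the 35% and the counts mean grade 3 only or grade 3 and above. The cost is one sentence and one definition. Conduct does not change, but the stated protection becomes weaker.
- **If the boundaries are not those intended:** the stopping rule needs an amendment, with its operating characteristics recalculated. Tighter boundaries also stop more often at lower complication rates. As an illustration only, at an assumed 20% rate, crossing either boundary has probability 11% as written and 29% with both one count lower.
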